#### **8.2.6. Pharmacodynamics**

Summary tables and graphical displays of observed values and changes from baseline in serum TTR will be used to assess the durability of suppression over the course of the study. Similar analyses will be performed for the secondary PD biomarker (vitamin A).

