## **1.5. Dose Selection and Rationale**

Clinical data demonstrate that multiple doses of ALN-TTRSC up to 10 mg/kg and fixed doses of 500 mg ALN-TTRSC have been safe and well-tolerated in healthy volunteers. In addition, similar PK, PD effects, and safety of ALN-TTRSC was observed in patients with TTR cardiac amyloidosis. Based on these data, the proposed 500 mg dose for this study is expected to result in sustained TTR reduction  $\geq 85\%$ . Patients enrolled in study ALN-TTRSC-003 will receive ALN-TTRSC at a fixed dose of 500 mg administered as 5 daily doses during Week 1, followed by weekly doses for the duration of the study through Day 1337 (or Early Termination [ET]). The longer dosing on the extension study is supported by the overall favorable benefit/risk profile of ALN-TTRSC to date and the absence of new findings in the ongoing long-term toxicology studies in rats and monkeys.

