### **2.2. Secondary Objectives**

Secondary objectives of this study are to assess the PD effect of long-term dosing of ALN-TTRSC on serum levels of TTR and the clinical effects of long-term dosing of ALN-TTRSC, including effect on mortality, hospitalization, and 6-MWT.

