### 3. STUDY PLAN

#### 3.1. Overall Design

Protocol ALN-TTRSC-003 is an open-label, extension study designed to evaluate the long-term safety, clinical activity, and PK of subcutaneously administered ALN-TTRSC in patients with TTR cardiac amyloidosis who previously completed the ALN-TTRSC-002 study.

[figure not shown]
The study will be conducted either at newly added study sites or at the same study sites where patients completed participation in Study ALN-TTRSC-002.

Eligible, consenting patients will receive 5 daily doses of ALN-TTRSC (Day 0, 1, 2, 3, and 4) and a dose at Day 7. They will then receive once weekly doses for the duration of the study through Day 1337 (or ET). Doses will be administered at the clinic during Days 0 through 7. Dosing after Day 7 may be administered at home by a healthcare professional trained in the protocol, or at the clinic if dosing coincides with the clinic visit for other assessments. At the discretion of the Investigator, after the Day 84 dosing visit, and if the patient has not experienced any severe adverse events or SAEs considered related to the study drug within the previous 12 weeks, patients/caregivers may be trained by the Investigator or qualified site staff in the administration of the study drug, according to the protocol dosing requirements.

Patients must be screened prior to administration of study medication under this protocol. Screening/Baseline assessments may be performed during several clinic visits. Patients must have completed the ALN-TTRSC-002 study to be eligible for this study. If the final (Day 90) visit in the ALN-TTRSC-002 study is within 28 days of the first dose administered in this study, then visit procedures performed as part of the Day 90 visit do not need to be repeated at the Screening/Baseline visit. If the final (Day 90) visit in the ALN-TTRSC-002 study occurred within 90 days of the first dose administered in this study, the echocardiogram and CMR do not need to be repeated at the Screening/Baseline visit. Assessments not conducted as part of the ALN-TTRSC-002 Day 90 visit must be completed at the Screening/Baseline visit.

Clinic visits will be performed for Screening/Baseline, dose initiation during Days 0 through 7, and then approximately every 12 weeks through the End of Study visit (or ET), and at approximately 28 days following the End of Study visit (or ET) for a Follow-up visit.

A schematic of the protocol design is presented in [Figure 1](#).

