### 4.2. Inclusion Criteria

Each patient must meet all of the following inclusion criteria during the Screening/Baseline period to be eligible for enrollment in this study:

1. Previously received and tolerated ALN-TTRSC in Study ALN-TTRSC-002; and completed Study ALN-TTRSC-002 through the Day 90 visit;
2. Adequate liver function, demonstrated by an AST and ALT  $\leq 2.5 \times$  ULN, total bilirubin  $< 2$  g/dL (34.2  $\mu$ mol/L), and albumin  $> 3$  g/dL ( $> 4.35$   $\mu$ mol/L);
3. Women of child-bearing potential (WOCBP) must have a negative pregnancy test, cannot be breast feeding, and must be willing to use a highly effective method of contraception (see Section 7.9.1) prior to Screening/Baseline, throughout study participation, and for 1 month after last dose administration;
  4. Males who agree to use appropriate means of contraception (see Section 7.9.2) throughout study participation until 1 month after last dose administration;
5. Patient, or patient's legal representative, is able and willing to provide written informed consent and the patient is willing to comply with the study requirements.

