### 4.3. Exclusion Criteria

Each patient must not meet any of the following exclusion criteria to be eligible for enrollment in the study:

1. Estimated Glomerular Filtration Rate  $< 20$  mL/min/1.73 m^2 (using the Modification of Diet in Renal Disease [MDRD] formula);
2. Uncontrolled hypertension;
3. Uncontrolled ischemic heart disease;
4. Uncontrolled clinically significant cardiac arrhythmia;
5. Untreated hypo- or hyperthyroidism;
6. Prior major organ transplant;
7. Known or suspected systemic bacterial, viral, parasitic, or fungal infection;
8. Seropositive for hepatitis B virus, hepatitis C virus (HCV) or known to be HIV positive;

9. Received an investigational agent other than tafamidis, diflunisal, doxycycline, or taurooursodeoxycholic acid, or an investigational device within 30 days prior to first dose of study drug;
10. Discontinued ALN-TTRSC-002 due to a treatment-related AE;
11. Metastatic cancer within the past 5 years;
12. Any conditions which, in the opinion of the Investigator, would make the patient unsuitable for enrollment or could interfere with the patient's participation in, or completion of, the study.
13. History of allergic reaction to an oligonucleotide or GalNAc.
14. Blinding Procedure

This is an open-label, multi-dose study; all patients will receive ALN-TTRSC. No blinding procedures are needed.

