### 8.2. Statistical Methodology

Statistical analyses will be primarily descriptive in nature. Adverse event summaries will include tabulations of all TEAEs, treatment-related AEs, SAEs, discontinuations due to AEs, and AEs of various grading severity.

Descriptive statistics will be provided for clinical laboratory data, vital signs data, and ECG interval data, presented as both actual values and changes from baseline relative to each on-study evaluation.

For categorical variables, summary tabulations of the number and percentage of patients within each category (with a category for missing data) will be presented. For continuous variables, the number of patients, mean, median, standard deviation, minimum, and maximum values will be presented.

A full statistical analysis plan will be finalized prior to database lock.

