#### **8.2.4. Clinical Activity Assessments**

Change from baseline by time point for 6-MWT will be summarized, where change from baseline is predose value (or final assessment from ALN-TTRSC-002, if a pre-dose assessment in this study is not required). Change from baseline will also be summarized where baseline is derived from predose assessments in ALN-TTRSC-002.

Frequency of hospitalization, cardiovascular hospitalization, and heart failure hospitalization will be summarized. All-cause mortality and cardiovascular mortality will be summarized using Kaplan-Meier curves.

Descriptive statistics will be presented for all clinical activity variables (NT-proBNP, troponin I, troponin T concentrations; selected echocardiography parameters; mBMI; NYHA classification; CMR imaging parameters). Patient reported QoL and disease burden will be assessed by summary statistics for the EQ-5D and KCCQ. Summary statistics will be provided for observed values and changes from baseline.

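### Must Section 8.2.6 name an untreated (ALN-TTRSC-002 predose) baseline for serum TTR and vitamin A, as Section 8.2.4 does for the six-minute walk?

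*Protocol*

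**What the plan says.** Prior treatment is a condition of entry. Inclusion criterion 1 in Section 4.2 reads: "Previously received and tolerated ALN-TTRSC in Study ALN-TTRSC-002; and completed Study ALN-TTRSC-002 through the Day 90 visit". Section 2.2 includes among the secondary objectives to "assess the PD effect of long-term dosing of ALN-TTRSC on serum levels of TTR".

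The pharmacodynamic analysis is in Section 8.2.6: "Summary tables and graphical displays of observed values and changes from baseline in serum TTR will be used to assess the durability of suppression". The period meant is the whole study, and vitamin A is to be handled similarly. The section does not say which value is the baseline.

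Section 8.2.4 is more specific for the six-minute walk. Its first baseline is the predose value in this study, or the last parent-study assessment where no new one is required. It then adds: "Change from baseline will also be summarized where baseline is derived from predose assessments in ALN-TTRSC-002".

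On detail still to come, Section 8.2 says: "A full statistical analysis plan will be finalized prior to database lock".

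**The concern.** Every entry value collected under this protocol comes after exposure. Table 1 schedules TTR at Screening/Baseline and again before the Day 0 dose. Section 3.1 allows parent-study results to stand in for Screening when the Day 90 visit falls within 28 days of the first dose here; in that case "visit procedures performed as part of the Day 90 visit do not need to be repeated at the Screening/Baseline visit". If baseline in Section 8.2.6 means one of these values, and TTR has not fully recovered by then, the reported change is smaller than the change from the untreated level. The shortfall would also vary between patients.

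The contrast with Section 8.2.4 sharpens the impression. The authors clearly considered prior exposure, because they added a pre-exposure reference for a functional test. They did not write the same for the protein the drug is designed to lower. Section 1.5 adds an expectation against which a reader may set the result: "the proposed 500 mg dose for this study is expected to result in sustained TTR reduction" of at least 85%, which is naturally read as relative to untreated. At stake would be a descriptive result for a secondary objective that appears weaker than the true effect.

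**Working it through.** **1. Does the text fix a wrong baseline?** Setting the analysis sections side by side:

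- Section 8.2 (general) and Section 8.2.3 (laboratory, vital signs, ECG): change from baseline, not defined.
- Section 8.2.4, six-minute walk: two baselines, both named.
- Section 8.2.4, all other clinical variables (biomarkers, echocardiography, KCCQ, EQ-5D and so on): change from baseline, not defined.
- Section 8.2.5 (healthcare utilization): not defined.
- Section 8.2.6 (TTR, vitamin A): not defined.

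The six-minute walk is the one variable given extra detail; TTR is treated like everything else. Sections 8.2.4 and 8.2.6 can both be followed as written. Nothing in Section 8.2.6 rules out the parent-study predose value as a baseline.

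**2. Does the choice of baseline affect the stated purpose?** Let a patient's TTR at two visits be a and b, and the baseline B.

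- Absolute change: (a − B) − (b − B) = a − b.
- Fraction of baseline remaining: (a/B) / (b/B) = a/b.

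B cancels in both. Whether suppression holds or fades within a patient is seen equally well from either baseline. Observed values do not involve B at all.

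**3. How large could the understatement be?** The protocol states no figure to reproduce, so this is illustration only. Inputs:

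- Untreated level = 1.
- On-treatment level = 0.15, from the 85% in Section 1.5, used only as an example.
- Residual suppression at entry = r, so the entry level is 1 − r. **The documents do not give r; it is assumed.**

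Formulas:

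- Percent reduction shown = 1 − 0.15/(1 − r).
- Absolute drop shown = 0.85 − r, against a true 0.85, so the relative shortfall is r/0.85.

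| r (assumed) | Percent reduction shown | Points below 85% | Relative shortfall in absolute drop |
|---|---|---|---|
| 0 | 1 − 0.15/1.0 = 85.0% | 0 | 0 |
| 0.10 | 1 − 0.15/0.9 = 83.3% | 1.7 | 0.10/0.85 = 11.8% |
| 0.20 | 1 − 0.15/0.8 = 81.3% | 3.8 | 0.20/0.85 = 23.5% |
| 0.30 | 1 − 0.15/0.7 = 78.6% | 6.4 | 0.30/0.85 = 35.3% |
| 0.50 | 1 − 0.15/0.5 = 70.0% | 15.0 | 0.50/0.85 = 58.8% |

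Percent reduction is exactly 1 point low when 0.15/(1 − r) = 0.16, that is, when entry TTR is 0.15/0.16 = 93.75% of untreated (r = 0.0625).

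**4. Can r be pinned down from the document?** No. The protocol gives neither TTR recovery data nor the parent-study dosing period. What it does say points towards some recovery. Patients must have completed the parent study through Day 90. Exclusion 9 in Section 4.3 bars "an investigational agent other than tafamidis, diflunisal, doxycycline, or taurooursodeoxycholic acid, or an investigational device within 30 days prior to first dose" of study drug; read literally, this covers ALN-TTRSC itself and implies at least 30 days off drug. So r may be small or nil, but the document cannot show that either. The last column is simply r divided by a constant and carries no information beyond the assumption.

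**The case for a change.** The strongest case for the concern is that the protocol did not leave baselines wholly to the analysis plan. It chose to name a pre-exposure reference for one secondary endpoint and not for another in the same tier, and the one left out is the measure most directly open to carry-over. Up to three post-exposure values could serve as the TTR baseline: Day 90 of the parent study, Screening, and Day 0 predose. For vitamin A, Table 1 as extracted shows only a Screening/Baseline entry before dosing, so a carried-over Day 90 result could be the only entry value. No untreated level is collected in this study, so change from untreated cannot be worked out from its own data.

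The facts in this stand, and the illustration is arithmetically right. What does not follow is that the protocol is wrong. Greater detail for one endpoint does not make less detail for another an error, and asking for the two to match is a drafting preference. Change from the untreated level is not a quantity that Section 8.2.6 names, nor does Section 2.2 define the pharmacodynamic effect that way. The 85% in Section 1.5 supports the dose choice and is not an analysis target. The untreated values also remain available: Section 8.2.4 already needs parent-study predose data, so the analysis plan can use them for TTR and vitamin A before database lock without new samples or visits.

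**Conclusion.** The concern does not hold as a fault in the protocol. Section 8.2.6 states nothing false, contradicts no other section and commits to no unsuitable baseline. It leaves a routine definition to an analysis plan that is promised but not shown here. Its stated purpose is met whichever baseline is used, and observed values are unaffected.

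The numerical effect is undetermined: none if TTR has recovered at entry, 1.7 to 6.4 percentage points for assumed residual suppression of 10% to 30%, and more if recovery is poorer. These figures assume a true reduction of 85% from untreated and a baseline taken at entry to this study; the protocol establishes neither. The study enrols about 25 patients, its analysis is primarily descriptive, and no test, threshold or decision rests on the TTR change.

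The conclusion is about the protocol alone. Whether the analysis plan names the baseline suitably cannot be judged from this document.

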#### **8.2.7. Pharmacokinetics**

Pharmacokinetic parameters will be calculated, when feasible, by noncompartmental methods using standard modeling software. Pharmacokinetic parameters will be summarized and presented, and mean ( $\pm$  standard error of the mean) concentration-time profiles will be generated by dose.

#### **8.2.8. Interim Analysis**

There is no formal interim analysis planned for this study. Interim data examinations may be performed, but these will be of a descriptive nature and will not involve any formal hypothesis testing.

#### **8.2.9. Missing Data**

For continuous and categorical variables, data will be analyzed as reported, unless otherwise specified. No imputation will be performed unless clearly identified.

For time-to-event variables, such as overall survival, subjects missing death will be right-censored.

## **9. STUDY MANAGEMENT**

The Investigator is accountable for the conduct of the trial. If any responsibilities are delegated, the Investigator should maintain a list of appropriately qualified staff to whom he/she has delegated specified significant trial related duties.

### **9.1. Data Handling and Quality Assurance**

#### **9.1.1. Case Report Forms**

The Investigator and designees agree to maintain accurate CRFs and source documentation as part of these case histories. Source documents are the originals of any documents used by the Investigator or hospital/institution that allow verification of the existence of the patient and substantiate the integrity of the data collected during the trial.

Alnylam will supply CRFs for each patient. Case report forms must be completed only by persons designated by the Investigator. Corrections must be made so as not to obliterate original data and must be identified and dated by the person who made the correction. All data entered into the CRF must also be available in the source documents. The Investigator will allow designated Alnylam representatives and regulatory bodies to have direct access to the source documents to verify the data reported in the CRFs.

Each completed CRF must be reviewed and signed by the Investigator or designee in a timely manner. The completed CRF will be the records maintained by Alnylam. A copy of the CRF will remain in the Investigator's files.

#### **9.1.2. Monitoring**

The clinical monitor, as a representative of Alnylam, has an obligation to follow the study closely. In doing so, the monitor will visit the Investigator and site periodically as well as maintain frequent telephone and written contact. The monitor will maintain current personal knowledge of the study through observation, review of study records and source documentation and discussion of the conduct of the study with the Investigator and staff.

All aspects of the study will be carefully monitored by Alnylam or its designee for compliance with applicable government regulations in respect to Good Clinical Practice (GCP) and current standard operating procedures.

#### **9.1.3. Inspections**

The Investigator will permit trial-related monitoring, audits and review by the IEC or IRB and/or Regulatory Authorities, providing direct access to source data/documents. The study may be subject to audit by Alnylam or its representatives or by regulatory authorities. If such an audit occurs, the Investigator must agree to allow access to the required patient records. In the event of an audit, the Investigator agrees to allow Alnylam, representatives from Alnylam, or regulatory agencies access to all study records.

## **9.2. Regulatory Guidelines**

This study will be performed in accordance with the clinical trial agreement, the protocol, all applicable government laws, regulations, and guidances where the study is being conducted including policies with foundations in the World Health Organization Declaration of Helsinki, the International Conference on Harmonization (ICH) of Technical Requirements for Registration of Pharmaceuticals for Human Use, the Health Insurance Portability and Accountability Act of 1996, and all other applicable medical privacy laws and regulations.

### **9.2.1. Independent Ethics Committee Institutional Review Board**

National regulations and ICH require that approval be obtained from an IEC or an IRB prior to participation of patients in research studies. Prior to the study onset, the protocol, any protocol amendments, informed consent forms (ICFs), advertisements to be used for patient recruitment, and any other written information regarding this study to be provided to a patient or patient's legal guardian must be approved by the IEC or IRB.

All IEC and IRB approvals must be dated and contain IEC/IRB Chairman or designee authorization and must identify the IEC/IRB (eg, name and address), the clinical protocol by title and/or protocol number, and the date of approval or favorable opinion was granted for the clinical research.

No drug will be released to the site to dose a patient until written IEC/IRB authorization has been received by Alnylam or designee.

The Investigator is responsible for obtaining continuing review of the clinical research at least annually or more often if specified by the IEC or IRB. The Investigator must supply Alnylam with written documentation of the approval of the continued clinical research.

The Investigator will make all attempts to ensure that the IEC or IRB is constituted and operates in accordance with Federal and ICH GCP and any local regulations.

### **9.2.2. Regulatory Authorities**

Regulatory authorities will receive the protocol, amendments, reports on SAEs, and the Integrated Clinical Trial Report according to national and any local regulations.

### **9.2.3. Modification of the Protocol**

Major changes in this research activity, except those to remove an apparent immediate hazard to the patient, must be reviewed and approved by Alnylam and the IEC or IRB that approved the study. Amendments to the protocol must be submitted in writing to the Investigator's IEC or IRB and the Regulatory Authority for approval prior to patients being enrolled under the amended protocol.

### **9.2.4. Informed Consent Form**

Written informed consent in compliance with ICH and local regulations will be obtained from each patient prior to undergoing any protocol-specific tests or procedures that are not part of routine care.

Alnylam will provide an ICF template to the Investigator for use in developing a site-specific ICF. Prior to submission of the site-specific ICF to the IEC/IRB, the site-specific ICF must be reviewed and approved by Alnylam. Any changes requested by the IEC/IRB must also be approved by Alnylam. The final IEC/IRB approved ICF must be provided to Alnylam. Revisions to the ICF required during the study must be approved by Alnylam, and a copy of the revised ICF provided to Alnylam.

Before recruitment and enrollment, each prospective patient will be given a full explanation of the study and be allowed to read the ICF. Once the Investigator is assured that the patient understands the commitments of participating in the study, the patient will be asked to sign and date the ICF. A copy of the fully signed and dated ICF will be given to the patient. The original will be maintained in the patient's medical record at the site. All active patients will sign an updated ICF if revisions are made to the ICF during the course of the study.

For patients who discontinue early and have provided consent, overall health status will be documented by telephone contact or non-patient contact follow-up (eg, medical record check) at the scheduled time points in an attempt to minimize the extent of missing data.

